2.2 VentaProst

2.2.1 Nonclinical Experience

Refer to the current Investigator's Brochure (IB) for details of nonclinical pharmacology and toxicology studies with VentaProst.

2.2.2 Clinical Experience

There have been no clinical trials to date with VentaProst.

2.2.3 Summary of Pharmacokinetic Results

Refer to the current IB for pharmacokinetic results with inhaled epoprostenol.

2.2.4 Summary of Clinical Results

There have been no clinical trials to date with VentaProst.

2.2.5 Summary of Known and Potential Risks of Inhaled Epoprostenol Administration

Safety of inhaled epoprostenol in cardiothoracic surgery patients is remarkable. In the reported literature to date, there were no reports of serious or life-threatening drug-related safety events. Due to its mechanism of action, inhaled epoprostenol may theoretically cause increased bleeding (anti-platelet mechanism) or systemic vasodilation consequent to spill over into the central circulatory system, but no such events have been reported. Some accounts of the use of inhaled prostacyclin in the chronic setting (e.g. iloprost for PAH) report transient events as listed on the approved product labeling. These include cough, headache, flushing, and an influenza-like syndrome. However, these types of events are unlikely to be reported due to sedation in the ICU setting.

2.2.6 Dosing Rationale for VentaProst

Literature on the current use of aerosolized epoprostenol shows a wide range and technically variable dosing for lowering PVR. Most of the experience is with continuous nebulization by commercially available nebulizers in various positions in mechanical ventilator circuits.

Unlike the commercially available nebulizer systems, VentaProst aerosolizes epoprostenol only during the inspiratory cycle of the ventilator, and administers very consistently sized aerosol droplets in close proximity to the endotracheal tube (ETT) of mechanically ventilated patients.

3. STUDY OBJECTIVES

3.1 Primary Objective

The primary objective of this study is to identify the relative dose equivalency between effective conventionally administered aerosolized Veletri and VentaProst doses.

3.2 Secondary Objectives

The secondary objectives are:

- To evaluate the safety and tolerability of VentaProst doses in a patient population post cardiac surgery with cardiopulmonary bypass (CPB)
- To demonstrate that VentaProst dose titration to achieve at least a 15% improvement in one or more hemodynamic parameters (as defined by the clinical team) is safe and effective
- To demonstrate the PD equivalence (based on cardiovascular parameters, indices of oxygenation, and ventilator support) of VentaProst doses to aerosolized Veletri doses
- To identify cardiovascular medications administered concomitantly with VentaProst
- To monitor ventilator support needed

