A review of published literature demonstrates that the use of inhaled epoprostenol in patients undergoing cardiothoracic surgery is safe and well tolerated. Doses of 10 – 100 ng/kg/min administered through a wide variety of conventional aerosol delivery methods led to improved hemodynamics (such as lowering of pulmonary arterial pressure [PAP] and pulmonary vascular resistance [PVR]), improved cardiac index (CI) and right ventricular ejection fraction (RVEF), easier separation from CPB, reduced intubation times, and shorter stays in the ICU.

The VentaProst nebulizer delivery platform is designed to accurately and precisely administer aerosol to the lungs of critically ill patients requiring support via mechanical ventilation and/or supplemental oxygen by nasal cannula. The intent is to standardize the critical components for consistent and quantifiable aerosolized epoprostenol delivery by mechanical ventilator and nasal cannula systems. Aerogen Pharma has evaluated various delivery systems used for conventional aerosol administration of epoprostenol to the lungs (in accordance with each site's standard of care practice guideline) and has estimated the equivalent dose by VentaProst.

The intent of Part I of the Phase 2a study is to demonstrate that the estimated VentaProst dose has the same hemodynamic effect as aerosolized Veletri at 50 ng/kg/min (in accordance with each site's standard of care guidelines). The assumption is that the hemodynamic response from the aerosolized Veletri dose will not change significantly with minor changes in dose (flat portion of the dose response curve). When patients are converted to VentaProst, a determination is made whether or not the hemodynamic response is similar by being at least as much as the response with the aerosolized epoprostenol dose. If the hemodynamic response with VentaProst is less than that of the aerosolized Veletri dose, the dose will be increased until a similar response is observed. VentaProst dosing will not be titrated downward to match the aerosolized Veletri hemodynamic response because of the possibility that the patients' requirements for pulmonary vasodilation may have improved since the start of aerosolized Veletri.

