4. OVERALL STUDY DESIGN AND PLAN

4.1 Part I

The first part of this study will be conducted in approximately 10 consented post-operative cardiothoracic surgery patients on CPB who are receiving aerosolized Veletri (in accordance with each site's standard of care guidelines) and who demonstrate at least a 15% improvement in one or more hemodynamic parameters (as defined by the clinical team) when treated with aerosolized Veletri. This part of the study is designed to demonstrate the dose equivalence between aerosolized Veletri and VentaProst using a patient's hemodynamic parameters, with the goal to determine the VentaProst dose necessary to achieve a hemodynamic response that is not less than 90% of the effect observed with 50 ng/kg/min aerosolized Veletri. Arterial oxygen saturation (SaO₂) must be maintained at or above the level obtained with aerosolized epoprostenol administration.

Qualifying patients will:

- Receive aerosolized Veletri 50 ng/kg/min in the OR/ICU
- Have hemodynamic parameters measured before and after aerosolized Veletri administration to determine changes

- *IF AT LEAST A 15% IMPROVEMENT IN ONE OR MORE HEMODYNAMIC PARAMETERS (AS DEFINED BY THE CLINICAL TEAM) IS SEEN WITH AEROSOLIZED VELETRI AFTER STABILIZATION IN THE ICU:*
 - Be administered VentaProst as follows: Setup VentaProst inline to the ventilator circuit, start nebulization, then stop conventional Veletri pump flow and nebulizer while still inline. Do not remove Veletri administration system until VentaProst administration is confirmed
- *IF LESS THAN A 15% IMPROVEMENT IN ONE OR MORE HEMODYNAMIC PARAMETERS (AS DEFINED BY THE CLINICAL TEAM) IS SEEN WITH AEROSOLIZED VELETRI AFTER STABILIZATION IN THE ICU:*
 - Not be administered VentaProst
- Receive a calculated equivalent starting dose of 17 ng/kg/min of VentaProst while still on mechanical ventilation
- Receive increases in the VentaProst dose in 20% increments (refer to the VentaProst Pharmacy Manual) every 15 minutes until at least 90% of the hemodynamic effect observed with 50 ng/kg/min aerosolized Veletri is achieved

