7. PHARMACODYNAMIC ASSESSMENTS

7.1 Primary Endpoint

Determination of the equivalent dose of VentaProst necessary to achieve a hemodynamic response that is not less than 90% of the effect observed with 50 ng/kg/min aerosolized Veletri.

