12.3 Analyses Sets

All patients who are enrolled in the study and who receive at least one dose of VentaProst will be included in the intent-to-treat (ITT) analyses of pharmacodynamic and safety data. All available data will be used and missing data will not be estimated or carried forward in any statistical summary or analyses.

Descriptive summary statistics include the number of patients, mean, median, percent coefficient of variation (% CV) (if required), standard deviation, and minimum and maximum values (quantitative variables) or the number of patients and percentages by category (qualitative variables). Changes will be assessed as the difference between baseline measurements and the appropriate post-dose measurements unless otherwise specified. Individual patient listings of data will also be provided to allow for review of all pharmacodynamic, safety, and tolerability parameters.

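### The design does not support the secondary objective to demonstrate PD equivalence: the hemodynamic match is a one-sided stopping rule, and no equivalence margin or interval is specified

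*Combined protocol and SAP*

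**What the plan says.** The Synopsis and Section 3.2 set the secondary objective: "To demonstrate the PD equivalence (based on cardiovascular parameters, indices of oxygenation, and ventilator support) of VentaProst doses to aerosolized Veletri doses". It spans three domains and has no numerical criterion of its own. The only number nearby belongs to the primary endpoint in Section 7.1, a response "not less than 90% of the effect observed with 50 ng/kg/min aerosolized Veletri".

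Section 4.1 has the Part I dose raised in 20% steps "every 15 minutes until at least 90% of the hemodynamic effect observed with 50 ng/kg/min aerosolized Veletri is achieved"; Sections 6.3.4.1 and 10.1.4.1 repeat the rule. Section 2.1 calls the response "similar by being at least as much as the response with the aerosolized epoprostenol dose" and adds that "VentaProst dosing will not be titrated downward to match the aerosolized Veletri hemodynamic response", because patients' need for pulmonary vasodilation may have lessened since Veletri was started. For SaO2, Section 4.1 says only that it "must be maintained at or above the level obtained with aerosolized epoprostenol administration".

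On analysis, Section 12.3 says "Descriptive summary statistics include the number of patients, mean, median" and goes on to other summaries and to listings. Section 12.5.2 gives the secondary endpoints analyses similar to the primary's, and Section 12.5.1 leaves the primary's detail to a SAP. Section 12.1 has that SAP final before database lock. The supplied text contains no SAP methods. Section 12.2 justifies about 10 patients per part on clinical grounds, with no margin, SD, alpha or power.

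**The concern.** An equivalence claim needs three things: a comparison that could come out either way, limits on both sides, and an interval or test set against those limits. For hemodynamics the comparison at the final dose lacks the first two, because patients arrive there by meeting the criterion and the criterion has no ceiling. For all three domains the protocol text lacks the third.

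The stake is how the study report is read. A table showing VentaProst responses close to or above Veletri's at the titrated dose could be presented as demonstrated equivalence, when much of that agreement would follow from the titration rule.

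**Working it through.** The plan states no power or precision figure for this objective, so there is none to reproduce. Everything below marked as assumed is illustrative.

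**1. Effect of stopping at a match.** The 0.90 floor is from Section 7.1. Assumed: a true VentaProst effect of 0.70 of Veletri's that does not change with dose; log-normal error in the observed ratio with SD 0.20 or 0.30; errors independent between looks; six looks.

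- One look: p = 1 − Φ(ln(0.90/0.70)/SD), with ln(0.90/0.70) = 0.251. SD 0.20 gives 1 − Φ(1.26) = 0.10; SD 0.30 gives 1 − Φ(0.84) = 0.20.
- Six looks: 1 − (1 − p)^6 = 0.48 and 0.74, from unrounded p of 0.104 and 0.201.
- Mean observed ratio at stopping, among those who stop: 0.99 and 1.08, although the truth is 0.70.

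Errors shared between looks, such as error in the single Veletri reading, would lower the six-look figures. They would not remove the selection.

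**2. Effect of a floor without a ceiling.** Assumed true ratio 1.5. The chance of meeting the floor at the first look is Φ(ln(1.5/0.90)/SD), with ln(1.5/0.90) = 0.511. This is Φ(2.55) = 0.995 at SD 0.20 and Φ(1.70) = 0.956 at SD 0.30. A response half as large again as Veletri's passes almost at once.

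**3. Where circularity stops.** Titration follows hemodynamic effect. SaO2 has a floor only; PaO2, FiO2 and ventilator pressures are not titrated to match. For these the gap is the missing margin and interval.

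**4. A reading the titration has not selected.** Table 1 footnote 10 and Section 10.1.4.1 require measurements before and after each VentaProst dose, so a reading at the fixed 17 ng/kg/min before any increase is already scheduled. Write B for the pre-Veletri value, T for the stabilized Veletri value and V for this VentaProst value. The comparison is (V − B) − (T − B) = V − T.

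With n = 10 the two-sided 90% CI half-width is t(0.95, 9)/√10 × SD = 1.833/3.162 × SD = 0.58 SD. For scale, at the entry minimum of a 15% Veletri improvement, 10% of the effect is 0.10 × 15 = 1.5 percentage points. Keeping the half-width within that needs an SD of the difference of at most 1.5/0.58 = 2.6 points. Larger Veletri effects relax this in proportion.

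**5. Why not a ratio.** A ratio of levels is misleading: complete loss of a 15% fall gives 1/0.85 = 1.18, inside limits of 0.80 to 1.25. A log ratio of changes is undefined when either change is zero or the signs differ.

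For a ratio of effects at a dose fixed in advance, true ratio 1, n = 10 and assumed log-SDs of 0.20, 0.30 and 0.40, the chance that a 90% CI falls within 0.80 to 1.25 is about 89%, 42% and 12%. Within 0.90 to 1.11 it is about 9% at SD 0.20. These figures must not be applied to a ratio of levels.

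**The case against.** The strongest reply is that a reader might infer that the objective cannot be met at all, or that no data could count against equivalence, and that neither follows. This is right. Titration can fail: Section 5.4.1 allows conversion back to Veletri for inadequate response, Section 5.4 lists lack of efficacy as a reason to discontinue, and the Synopsis plans to summarize success or failure on the PD goals. The matched dose is held at least 15 minutes with measurements scheduled during stabilization, so a later reading could contradict the match. Oxygenation and ventilator measures could also disagree.

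A reader might also infer that nothing beyond descriptive statistics will ever be done. The documents support only that the protocol specifies no more; a SAP could add intervals. It could not undo selection of a dose because it matched. Since the study is open label (Section 6.5), a margin chosen shortly before database lock could be set with results in view.

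The one-sided rule is deliberate, with its reason given in Section 2.1. That explains the rule but does not turn a floor into equivalence.

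Finally, the 17 ng/kg/min reading is not a clean comparison. Treatment order is fixed, patients may change over time, and only patients with at least a 15% observed Veletri response enter. That selection can bias the comparison against VentaProst through regression to the mean. These limits stand and must be disclosed.

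**Conclusion.** The concern holds in limited form. The word demonstrate promises more than the specified design supports. For hemodynamics, agreement at the final dose among patients who reach the criterion is a result of the stopping rule, and the rule is one-sided. For oxygenation and ventilator measures, the protocol specifies no equivalence margin or interval. This conclusion rests on the protocol text and not on the assumed SDs; the 48% to 74% and the power figures only give a sense of size.

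It would go too far to read this as undermining the primary objective. Identifying the dose that meets the 90% criterion is a dose-finding task, for which titrating to a criterion is a coherent method. The point concerns one secondary objective in a small Phase 2a study and should be corrected, since correction is cheap.

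**What to change.** - In the Synopsis and Section 3.2, reword the objective to: estimate the PD response of VentaProst relative to aerosolized Veletri.
- In Section 12.5.2 and the SAP, before any Part I results are reviewed, name the parameters. For each, make the main comparison the within-patient difference between the change from the pre-Veletri value on VentaProst at 17 ng/kg/min, read before any increase, and the change from the same value on stabilized Veletri, with a two-sided 90% CI. Name the pre-Veletri value explicitly, because Sections 10.1.2 and 12.4 define the hemodynamic baseline as pre-surgery.
- Report the post-titration match as a check of the titration, with the number of patients who did not reach 90% or were converted to Veletri.
- State the limits: fixed order, possible change over time, and selection on at least a 15% Veletri response.
- Reconcile Section 2.1 (at least as much as Veletri) with Section 7.1 (not less than 90%).

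The comparison uses measurements already scheduled and changes no dosing. The cost is a more modest claim and a small amount of extra analysis.

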4. OVERALL STUDY DESIGN AND PLAN

4.1 Part I

The first part of this study will be conducted in approximately 10 consented post-operative cardiothoracic surgery patients on CPB who are receiving aerosolized Veletri (in accordance with each site's standard of care guidelines) and who demonstrate at least a 15% improvement in one or more hemodynamic parameters (as defined by the clinical team) when treated with aerosolized Veletri. This part of the study is designed to demonstrate the dose equivalence between aerosolized Veletri and VentaProst using a patient's hemodynamic parameters, with the goal to determine the VentaProst dose necessary to achieve a hemodynamic response that is not less than 90% of the effect observed with 50 ng/kg/min aerosolized Veletri. Arterial oxygen saturation (SaO₂) must be maintained at or above the level obtained with aerosolized epoprostenol administration.

Qualifying patients will:

- Receive aerosolized Veletri 50 ng/kg/min in the OR/ICU
- Have hemodynamic parameters measured before and after aerosolized Veletri administration to determine changes

- *IF AT LEAST A 15% IMPROVEMENT IN ONE OR MORE HEMODYNAMIC PARAMETERS (AS DEFINED BY THE CLINICAL TEAM) IS SEEN WITH AEROSOLIZED VELETRI AFTER STABILIZATION IN THE ICU:*
 - Be administered VentaProst as follows: Setup VentaProst inline to the ventilator circuit, start nebulization, then stop conventional Veletri pump flow and nebulizer while still inline. Do not remove Veletri administration system until VentaProst administration is confirmed
- *IF LESS THAN A 15% IMPROVEMENT IN ONE OR MORE HEMODYNAMIC PARAMETERS (AS DEFINED BY THE CLINICAL TEAM) IS SEEN WITH AEROSOLIZED VELETRI AFTER STABILIZATION IN THE ICU:*
 - Not be administered VentaProst
- Receive a calculated equivalent starting dose of 17 ng/kg/min of VentaProst while still on mechanical ventilation
- Receive increases in the VentaProst dose in 20% increments (refer to the VentaProst Pharmacy Manual) every 15 minutes until at least 90% of the hemodynamic effect observed with 50 ng/kg/min aerosolized Veletri is achieved

Once a VentaProst dose equivalence has been achieved, patients will be weaned from VentaProst. VentaProst weaning will occur from mechanical ventilation only. If the patient has been extubated and is on institution's standard of care delivery system for administering aerosolized Veletri, weaning will occur in accordance with each site's standard of care guidelines for weaning of aerosolized Veletri. The table below shows the typical weaning steps for aerosolized Veletri from mechanical ventilation. If weaning from VentaProst occurs while on mechanical ventilation, doses will be decreased in 20% increments of the VentaProst equivalent dose.

Weaning Guideline

Aerosolized Veletri (from Ventilator)	VentaProst (from Ventilator)
50 ng/kg/min	Dose Equivalence to aerosolized Veletri 50 ng/kg/min
40 ng/kg/min	80% of Dose Equivalence
30 ng/kg/min	60% of Dose Equivalence
20 ng/kg/min	40% of Dose Equivalence
10 ng/kg/min	20% of Dose Equivalence

Patients on mechanical ventilation will be weaned from VentaProst slowly due to concern that VentaProst is providing significant clinical benefit and to avoid a rebound effect. Doses will be decreased in increments of 20% of the VentaProst equivalent dose, with a minimum of 30 minutes between changes, down to 20% of the dose before discontinuation. The VentaProst weaning process should occur in isolation to other

treatment changes (no changes in inotropes, pressors or vasodilators). Patients will be observed closely before, during, and after dosing changes. In the event patients demonstrate signs of hemodynamic instability (changes in combined hemodynamic parameters) or a decrease in oxygenation indicated by either arterial or central blood oxygenation saturation during downward titration, the VentaProst dose will be returned to its previous level. Once patients have been stable for at least 15 minutes, repeat attempts at dose reduction may be undertaken. The process will continue until patients are fully weaned from VentaProst. A final PD measurement will be collected 15 to 30 minutes after discontinuation of VentaProst.

Patients will be monitored for safety and PD efficacy throughout the aerosolized Veletri and VentaProst administrations.

4.2 Part II

The second part of the study will be conducted in approximately 10 consented cardiothoracic surgical patients on CPB with perioperative pulmonary hypertension (mPAP > 25 mm Hg). This part of the study is designed to establish a dose response relationship of VentaProst to PD effect by dose escalation in these patients. The goal will be to determine the VentaProst dose necessary to achieve at least a 15% improvement in one or more hemodynamic parameters (as defined by the clinical team).

Hemodynamic measurements will be taken prior cardiac surgery (after induction) with CPB, prior to dosing with VentaProst, and after each dose titration step.

Qualifying patients will:

- Receive a starting dose of 3.4 ng/kg/min of VentaProst
- Have hemodynamic parameters monitored and recorded
- Receive increase in the VentaProst dose in 3.4 ng/kg/min increments (refer to VentaProst Pharmacy Manual)
 - *IF A GREATER THAN A 15% IMPROVEMENT IN ONE OR MORE HEMODYNAMIC PARAMETERS (AS DEFINED BY THE CLINICAL TEAM) IS SEEN WITH THE INITIAL VENTAPROST DOSE, but NO additional clinically meaningful change is seen with this first dose escalation:*
 - Have the VentaProst dose reduced to the initial dose level
 - *IF A GREATER THAN A 15% IMPROVEMENT IN ONE OR MORE HEMODYNAMIC PARAMETERS (AS DEFINED BY THE CLINICAL TEAM) IS SEEN WITH THE INITIAL VENTAPROST DOSE, but AN additional clinically meaningful change is seen with the first dose escalation:*
 - Continue to receive VentaProst in increasing steps of 3.4 ng/kg/min every 5 to 15 minutes as clinically indicated until no further improvements in one or more hemodynamic parameters are achieved or until dose-limiting pharmacological effects are elicited or a tolerance limit to VentaProst is established.

- *IF A LESS THAN A 15% IMPROVEMENT IN ONE OR MORE HEMODYNAMIC PARAMETERS (AS DEFINED BY THE CLINICAL TEAM) IS SEEN WITH FIRST DOSE INCREASE:*
 - Continue to receive VentaProst in increasing steps of 3.4 ng/kg/min every 5 to 15 minutes as clinically indicated until no further improvements in one or more hemodynamic parameters are achieved or until dose-limiting pharmacological effects are elicited or a tolerance limit to VentaProst is established.
 - Reduce the VentaProst dose to the previous dose level (after the VentaProst dose has stabilized) at which the one or more hemodynamic parameters showed maximum improvement. The VentaProst dose level will remain at this setting until clinical conditions determine the need for changing the dose.

Arterial and central venous blood oxygenation parameters will also be considered in the titration process.

Hemodynamic, oxygenation, and ventilator parameters will be obtained at the time of each VentaProst dose adjustment in the ICU.

Patients requiring post-operative support with epoprostenol will be allowed to continue on VentaProst treatment in the ICU as long as they are still on mechanical ventilation. For weaning, doses will be decreased in increments of 20% of the VentaProst equivalent dose, with a minimum of 30 minutes between changes, down to 20% of the dose before discontinuation (see Section 4.1, Weaning Guideline in Part I above). If the patient is extubated and placed on institution's standard of care delivery system for administering aerosolized Veletri, weaning from aerosolized Veletri will follow each institution's guideline.

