4.6 End of Treatment

In both Part I and Part II, final PD measurements (based on hemodynamic parameters, indices of oxygenation, and ventilator support) will be collected 15 to 30 minutes after discontinuation of VentaProst. End of study physical examination, vital signs/weight, 12-lead ECG, clinical laboratory testing, serum pregnancy testing, hemodynamic parameters, oxygenation measurements, ventilator parameters, adverse events monitoring, and concomitant medications will also be obtained at the end of treatment.

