- Measure hemodynamic, oxygenation, and ventilator parameters before and at 15 to 30 minutes after each VentaProst dose adjustment and at 15 to 30 minutes after discontinuation of VentaProst
- Record all concomitant medications
- Record AEs

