12.2 Determination of Sample Size

The number of patients has been selected to enable an adequate clinical assessment of pharmacodynamics, safety, and tolerability parameters without presenting undue risk to a large number of patient's exposure to this investigational product.

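### Part II seeks a dose response from an uncontrolled upward titration, and Section 12 names no analysis that separates dose from elapsed time, although weaning and off-drug readings that could help are already scheduled

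*Combined protocol and SAP*

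**What the plan says.** Section 4.2 gives the purpose of Part II as follows: "This part of the study is designed to establish a dose response relationship of VentaProst to PD effect by dose escalation in these patients". Its goal is to "determine the VentaProst dose necessary to achieve at least a 15% improvement in one or more hemodynamic parameters", in "approximately 10 consented cardiothoracic surgical patients on CPB with perioperative pulmonary hypertension". Patients start at 3.4 ng/kg/min and go up by the same amount every 5 to 15 minutes (Sections 4.2 and 10.2.3.1). After the plateau the dose goes back to an earlier level. There is no concurrent control.

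Section 10.2.2 sets the hemodynamic baseline before surgery, after induction. Section 12.3 measures change from baseline unless otherwise specified. A reading just before VentaProst is also taken (Section 4.2; Table 2, footnote 5).

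During weaning, Section 10.2.3.2 asks sites to "Measure hemodynamic, oxygenation, and ventilator parameters before and at 15 to 30 minutes after each VentaProst dose adjustment". Section 4.6 adds final measurements that "will be collected 15 to 30 minutes after discontinuation of VentaProst".

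Section 12.5 restates the endpoints and says the secondary ones will be analysed like the primary one. Sections 12.1 and 12.5.1 leave details to a SAP, and the document supplied contains no separate SAP text. Section 12.2 gives no statistical basis for the number of patients.

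**The concern.** When every patient climbs the same ladder in the same order, a higher dose is also a later reading. If pulmonary hemodynamics change by themselves in the hour after the drug is started, that change appears as dose response, can move a patient across the 15% line, and can be taken for a further improvement that justifies another step. More patients on the same schedule would not cure this.

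The protocol allows for such a change elsewhere. Section 2.1 explains why Part I does not titrate downward by "the possibility that the patients' requirements for pulmonary vasodilation may have improved since the start of aerosolized Veletri". Nothing in Part II or Section 12 makes a matching allowance.

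Two results are at stake: the dose-response description itself, and the secondary objective that titration to a 15% improvement is safe and effective. The reference point adds to the difficulty, because a change measured from a pre-surgery baseline also contains the effects of surgery and bypass.

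**Working it through.** The plan states no power, standard deviation or dose-response figure, so there is nothing to reproduce. The check builds the Part II schedule and asks what it can separate.

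**Inputs from the documents.** Start and step 3.4 ng/kg/min, interval 5 to 15 minutes (4.2); one step back (4.2, 10.2.3.1); weaning in 20% decrements at least 30 minutes apart (10.2.3.2); off-drug reading 15 to 30 minutes after stopping (4.6); half-life about 3 minutes (2.1).

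**Assumptions not in the documents.** Three, five or eight upward steps; a hold of 0 to 24 hours before weaning; the rate and shape of any spontaneous change. Five steps reach 5 × 3.4 = 17 ng/kg/min.

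**1. Upward leg alone.** With equal intervals the dose-time correlation is r = 1.00, and the variance inflation factor, VIF = 1/(1 − r²), is infinite. With intervals drawn at random between 5 and 15 minutes, median r is 0.994 to 0.997 and median VIF about 91 to 160.

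**2. Size of a drift-only response.** Five steps take 25 to 75 minutes. Drift by step five = hourly rate × minutes/60:

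| Assumed drift | after 25 min | after 75 min |
|---|---|---|
| 2%/h | 0.8% | 2.5% |
| 5%/h | 2.1% | 6.2% |
| 10%/h | 4.2% | 12.5% |

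To reach 15% with no drug effect, the rate must be 15/(25/60) = 36%/h with 5-minute steps, 15/(50/60) = 18%/h with 10-minute steps, or 15/(75/60) = 12%/h with 15-minute steps. With eight steps the range is 22.5 down to 7.5%/h.

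**3. Adding readings already scheduled** (five steps, 10-minute intervals). The step-back alone gives VIF 9.1 (3.3 for three steps, 26 for eight). Adding weaning and off-drug readings gives r = −0.33 to −0.35 and VIF 1.12 to 1.14.

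**4. Is the last reading really off drug?** 15/3 = 5 and 30/3 = 10 half-lives, so 0.5⁵ ≈ 3% to 0.5¹⁰ ≈ 0.1% of drug remains. It is close to a zero-dose reading.

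**5. Does a time term remove the false effect?** Set the true drug effect to zero and fit by least squares; results are percentage points at 17 ng/kg/min, with 10-minute steps unless stated.
- Linear drift of 6%/h: the upward leg alone gives a false 5.0; both legs with dose and linear time give 0. Pooling both legs without a time term gives −7.8 (hold of 15 minutes), so the time term is essential.
- Recovery that levels off, y = 20(1 − 0.5^(t/60)), t in minutes: upward leg 8.8; dose plus linear time still leaves 5.5 to 7.3.
- The same curve with 15-minute steps and weaning from 17 ng/kg/min: upward leg 11.5; dose plus linear time leaves 5.8, 6.8 and 7.5 for holds of 0, 1 and 12 hours. A quadratic time term shrinks the remainder for the two short holds but enlarges it for the 12-hour hold.
- Half-time 240 minutes: upward leg 2.7; 0.7 to 2.3 left.

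**6. Can the same dose be compared going up and coming down?** A 20% weaning step from stable dose D equals a multiple k of 3.4 only if 0.2 × D = 3.4k, that is D = 17k. From 17 the weaning doses are 13.6, 10.2, 6.8 and 3.4. From 13.6 they are 10.88, 8.16, 5.44 and 2.72, none of which was given on the way up.

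**The case against.** A reader might infer that Part II will use upward readings only. The documents do not say so. The titration includes a step-back, Section 6.3.3.2 speaks of titration in both directions, the synopsis says the readings around each dose change are meant to show its effect, and Section 12.3 says all available data will be used. Section 12.5 assigns no role to any particular reading, ascending or descending, and defers to a SAP. This objection stands: the fault is that no separating analysis is named, not that one is ruled out.

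A reader might also infer that the bias favours the product. That would need a spontaneous improvement during titration, and no figure supports its rate or direction. Section 2.1 mentions only a possibility, for Part I patients whose Veletri period is listed as 24 hours or more, not for a titration of 25 to 75 minutes. This too stands.

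Third, one might infer that the weaning data settle the matter. Step 5 shows that they need not. Weaning begins when the patient is judged stable, takes place only on the ventilator, and goes back up a level on instability, so these readings are selected by recovery. Section 10.2.3.2 also names a rebound effect on withdrawal. Rebound would make the off-drug comparison overstate the drug effect.

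Finally, this is a descriptive Phase 2a study, and a model in about 10 patients can only be supportive. That is fair, but the stated purpose is still to establish a dose response, and the readings that would help are already being taken.

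**Conclusion.** The point holds in a limited form. On the upward leg, dose and time are collinear or nearly so, and the protocol names no analysis to separate them. A rising response there cannot by itself be attributed to dose. This follows from the schedule and needs no assumption about recovery.

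How much it matters is unknown. Drift alone reaches 15% by step five only at 12 to 36% per hour; at an assumed 2 to 10% per hour it supplies 0.8 to 12.5 points. These rates are illustrations.

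Adding step-back, weaning and off-drug readings brings the VIF to about 1.1 for five steps. It removes the false effect fully only if the time trend is modelled correctly; with levelling recovery more than half of it can remain. The pre-dose and off-drug comparisons bracket the drug effect only if recovery runs one way and there is no rebound. The change is worth making before the SAP is final, but the plan contains no error of calculation here.

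**What to change.** In Section 12.5 and the SAP:

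1. Use the reading just before VentaProst, not only the pre-surgery baseline, as the reference for the Part II change and the 15% result. Show beside it, for each patient, the change against the reading 15 to 30 minutes after discontinuation.
2. Add a supportive within-patient analysis of all on-ventilator VentaProst readings (pre-dose, ascending, step-back, weaning, off-drug), with actual dose in ng/kg/min and elapsed time as separate terms. Show how the dose slope changes under a non-linear time term.
3. Plot ascending and descending readings against actual dose for each patient. A table matched on dose would line up only where the stable dose is 17 ng/kg/min or a multiple of it.
4. State the limits. Weaning readings come only from patients weaned on the ventilator and judged stable. Patients moved to Veletri at extubation have no off-drug value and should be listed. Rebound could make the off-drug comparison overstate the effect, so the two references are not a guaranteed bracket.

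The cost is a little more analysis and a wider interval on the dose slope. All readings are already scheduled, and no dose, schedule or clinical rule changes.
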